Replication of Prasugrel versus Clopidogrel in Patients with Acute Coronary Syndromes (TRITON-TIMI 38 Trial)

January 13, 2020

1. RCT Details

This section provides a high-level overview of the RCT that the described real-world evidence study is trying to replicate as closely as possible given the remaining limitations inherent in the healthcare databases.

1.1 Title

Prasugrel versus Clopidogrel in Patients with Acute Coronary Syndromes (TRITON-TIMI 38 trial)

1.2 Intended aim(s)

To compare prasugrel, a new thienopyridine, with clopidogrel, we randomly assigned 13,608 patients with moderate-to-high-risk acute coronary syndromes with scheduled percutaneous coronary intervention to receive prasugrel (a 60-mg loading dose and a 10-mg daily maintenance dose) or clopidogrel (a 300-mg loading dose and a 75-mg daily maintenance dose), for 6 to 15 months.

1.3 Primary endpoint for replication and RCT finding

The primary efficacy end point was death from cardiovascular causes, nonfatal myocardial infarction, or nonfatal stroke. The key safety end point was major bleeding.

1.4 Required power for primary endpoint and noninferiority margin (if applicable)

We calculated that a total of 875 primary end points would be required for the study to have a 90% power to detect a 20% reduction in the relative risk of the primary end point among patients with unstable angina or non–ST-elevation myocardial infarction receiving prasugrel, as compared with clopidogrel.

1.5 Primary trial estimate targeted for replication

HR = 0.81 (95% CI 0.73–0.90) comparing prasugrel to clopidogrel (Wiviott et al., 2007)

2. Person responsible for implementation of replication in Aetion

[name]. implemented the study design in the Aetion Evidence Platform. S/he is not responsible for the validity of the design and analytic choices. All implementation steps are recorded and the implementation history is archived in the platform.

[figure not shown]
Effectiveness research with Real World Data to support FDA's regulatory decision making: Protocol Template

3. Data Source(s)

United/Optum, MarketScan

4. Study Design Diagram

The study design diagram visualizes key aspects of the longitudinal study design for expedited review.

5. Cohort Identification

5.2 Important steps for cohort formation

New users (defined as no use in 180 days prior to index date) of an exposure and a comparator drug will be identified.

5.2.1 Eligible cohort entry dates

Market availability of prasugrel in the U.S. started on 2009-07-10.

- For Marketscan: 2009-07-10 to 2017-12-31 (end of data availability).
- For Optum: 2009-07-10 to 2019-03-31 (end of data availability).

5.2.2 Specify inclusion/exclusion criteria for cohort entry and define the index date

Inclusion and exclusion criteria were adapted from the trial as closely as possible. Definitions for all inclusion/exclusion are provided in **Appendix A** and are summarized in the flowcharts below.

5.3 Flowchart of the study cohort assembly

	Optum		Mar	ketScan
	Less Excluded Patients	Remaining Patients	Less Excluded Patients	Remaining Patients
All patients		75,524,500		191,990,035
Patients meeting the cohort entry criteria of moderate to high risk Acute Coronary Syndrome undergoing PCI procedure	-75219388	305,112	-191556394	433,641
Patients with sufficient enrollment period in the claims database	-41910	263,202	-120017	313,624
Patients with moderate to high risk Acute Coronary Syndrome	-144114	119,088	-165792	147,832
Patients initiating clopidogrel 75mg or prasugrel 10mg within 14 days of discharge of PCI hospitalization	-56497	62,591	-54511	93,321

Patients without history of hemorrhagic stroke	-349	62,242	-392	92,929
Patients without intracranial neoplasm, AV malformation, or aneurysm	-186	62,056	-202	92,727
Patients without ischemic stroke occurring 90 days prior to PCI hospitalization	-163	61,893	-255	92,472
Patients with sufficient claims enrollment after PCI hospital discharge	-483	61,410	-1191	91,281
Parent: Final cohort		61,410		91,281
Did not meet cohort entry criteria	-80	61,330	0	91,281
Excluded due to insufficient enrollment	0	61,330	0	91,281
Patients with no prior use of clopidogrel	-3135	58,195	-3653	87,628
Patients with no prior use of prasugrel	-535	57,660	-958	86,670
Patients without qualification in >1 exposure category	-18	57,642	-20	86,650
Patients age 18 years or older	-2	57,640	0	86,650
Patients without cardiogenic shock during PCI hospitalization	-1811	55,829	-2457	84,193
Patients without refractory ventricular arrhythmias	-5341	50,488	-7235	76,958
Patients without New York Heart Association Class IV congestive heart failure	-416	50,072	-265	76,693
Patients without active internal bleeding or history of bleeding diathesis	-3974	46,098	-3739	72,954
Patients without thrombocytopenia (platelet count of less than 100,000/mm3)	0	46,098	0	72,954
Patients without anemia (hemoglobin <10 g/DI)	-886	45,212	-2039	70,915
Patients without a claim for thienopyridine 5 days or less before PCI hospitalization	-1	45,211	-1	70,914
Patients without daily treatments with NSAIDs or COX-2 inhibitors	-394	44,817	-654	70,260
Patients without concomitant medical illness that is potentially associated with reduced survival	-687	44,130	-235	70,025
Patients without severe hepatic dysfunction	-1755	42,375	-2041	67,984
Patients without issues on poor treatment compliance including alcoholism, mental illness, or drug dependence	-2927	39,448	-1981	66,003
Final cohort		39,448		66,003

6. Variables

6.1 Exposure-related variables:

Study drug:

The study exposure of interest is initiation of Prasugrel. Initiation will be defined by no use of Prasugrel or a comparator in the prior 6 months before treatment initiation (washout period).

Effectiveness research with Real World Data to support FDA's regulatory decision making: Protocol Template

Comparator agents:

- Initiators of prasugrel 10mg will be compared to initiators of-
 - Clopidogrel 75mg

6.2 Preliminary covariates:

- Age
- Sex
- Combined Comorbidity Index (CCI), measured over the default baseline covariate assessment period, defined as 180 days prior to and including index date

Covariates listed above represent only a small subset of covariates that will ultimately be controlled for in the design and analysis. We use the covariates above only for initial feasibility analyses to judge whether there is likely to be sufficient overlap between treatment groups to proceed with the study. Remaining covariates are defined only after the study has passed the initial feasibility analysis and the initial power assessment and are listed in Table 1 (Appendix B).

6.3 Outcome variables and study follow-up:

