6.3.2 Study follow-up

Both as-treated (AT) and intention-to-treat (ITT) analyses will be conducted with treatment defined as the index drug on the day of cohort entry. Because adherence in the real-world databases is expected to be much worse than in the trial, the AT analysis is the **primary** analysis, as it targets the relative hazard of outcomes on treatment.

For the AT analyses, the follow-up will start the day after initiation of prasugrel and comparator and will continue until the earliest date of the following events:

- The first occurrence of the outcome of interest, unless otherwise specified for selected outcomes,
- The date of end of continuous registration in the database,
- End of the study period,
- Measured death event occurs,
- Nursing home admission
 - Nursing home admissions are considered a censoring event because the data sources utilized typically provide little to no data on a patient, particularly on drug utilization, after admission. We will utilize this as an exclusion reason for cohorts for the same reason.
- The date of drug discontinuation, defined as the date of the last continuous treatment episode of the index drug (prasugrel and comparator) plus a defined grace period (i.e., 30 days after the end of the last prescription's days' supply in main analyses).
- The date of augmentation or switching from an exposure to a comparator
- Initiation of ticagrelor

For the ITT analyses, the censoring based on the augmentation/switching and treatment discontinuation will be replaced with a maximum allowed follow-up time of 365 days.

7. Initial Feasibility Analysis

Aetion report links:

Optum: https://bwh-dope.aetion.com/projects/details/989/results/46156/result/0 Marketscan: https://bwh-dope.aetion.com/projects/details/990/results/46157/result/0

Date conducted: December 15, 2019

Complete Aetion feasibility analysis using age, sex, and CCI as the only covariates and the primary endpoint (Section 6.3.1) as the outcome. No measures of association will be computed nor will incidence rates stratified by treatment group.

- Report patient characteristics by treatment group
- Report summary parameters of the overall study population
- Report median follow-up time by treatment group
- Report reasons for censoring in the overall study population

8. Initial Power Assessment

Aetion report links:

Optum: https://bwh-dope.aetion.com/projects/details/989/results/46159/result/0

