		ICD-9: 433.xx, 434.xx, 436.xx ICD-10: I63.xx I65.xx I66.xx	in Routine Clinical Care: A First Analysis from the Empagliflozin Comparative Effectiveness and Safety (EMPRISE) Study." Circulation. 2019 Apr 8. doi: 10.1161/CIRCULATIONAHA.118.039177
9	International normalized ratio known to be greater than 1.5 at the time of screening	N/A	
10	Platelet count of less than 100000/mm3 at the time of screening	Measured during index hospitalization in inpatient setting, any position Thrombosytopenia: ICD-10: D99, Bobd-4x, D69.5x, D69.2x, D69.3x ICD-9: 287.3x, 287.4x	
11	Anemia (hemoglobin b10 g /dL) at the time of screening	Meesured during Index hospitalization in Inpetient setting, any position ICD-9: 280.0 Iron deficiency anemia secondary to blood loss (chronic) 285.1 Acute most hemorrhaeic anemia! 285.9 (Anemia unspecified)	
11	Anemia (hemoglobin b $10\mathrm{g/dL}$) at the time of screening		

	Prior/concomitant therapy exclusion criteria		
12	One or more doses of a thienopyridine 5 d or less before PCI	Prescription for following drugs 5 days prior to Index hospitalization Clopidogrel, prasugrel, or ticlopidine	
13	Oral anticoagulation or other antiplatelet therapy that cannot be safely discontinued for the duration of the study	N/A	
	Daily treatment with nonsteroidal antiinflammatory drugs (NSAIDs) or cyclooxygenase-2 inhibitors (COX-2 inhibitors)	More than 150 days of supply out of 180 days prior to drug initiation NSAID: aspirin, ibuprofen, naproxen >> OTC cannot be captured COX-2 inhibitors: celecoxib	
	General exclusion criteria		
15		N/A	
16	Employed by Eli Lilly and Company; Ube Industries Limited, Dalichi Sankyo Co.; The TIMI Study Group; Quintiles	N/A	
17	Treatment within the last 30 d with an investigational drug or are presently enrolled in another drug or device study	N/A	
18	Previously completed or withdrawn from this study or any other study investigating prasugrel	N/A	
19	Women who are known to be pregnant, have given birth within the past 90 d, or are breast-feeding	N/A	
20		Following Index score measured 180 days prior to drug Initiation Combined comorbidity index CCI >=10	Gagne, Josh J et. al. "'A combined comorbidity score predicted mortality in elderly patients better than existing scores." J Clin Epidemiol. 2011 Jul;64(7):749-59. doi: 10.1016/j.jclinepi.2010.10.004. Sun, Jenny W et. al. "Validation of the Combined Comorbidity Index of Charlson and Elixhauser to Predict 30-Day Mortality Across ICD-9 and ICD-10." Med Care. 2018

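### The new-user washout omits ticagrelor although the primary as-treated analysis censors at it; the effect is probably small and the gap is cheap to close

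*Combined protocol and SAP*

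**What the plan says.** **New use.** Section 5.2: "New users (defined as no use in 180 days prior to index date) of an exposure and a comparator drug will be identified". Section 6.1: "Initiation will be defined by no use of Prasugrel or a comparator in the prior 6 months before treatment initiation (washout period". The only comparator that 6.1 lists is "Clopidogrel 75mg".

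**Flowchart (5.3).** There are two prior-use steps, "Patients with no prior use of clopidogrel" and "Patients with no prior use of prasugrel". A step for patients qualifying in both exposure groups follows. None names ticagrelor.

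**Appendix A.** Exclusion 12 covers "Clopidogrel, prasugrel, or ticlopidine" in the 5 days before the index hospitalization. The trial's exclusion 13, "Oral anticoagulation or other antiplatelet therapy that cannot be safely discontinued for the duration of the study", is marked N/A.

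**Follow-up (6.3.2).** The as-treated analysis is primary, and "Initiation of ticagrelor" is one of its censoring events. Nursing home admission is also a censoring event, and the same section makes it a cohort exclusion for the same reason. Ticagrelor has no matching baseline rule.

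**The concern.** By censoring at ticagrelor, the plan treats it as a third competing treatment that ends valid on-treatment time. The entry rules do not treat it that way: a fill just after entry ends follow-up, while a fill just before entry has no consequence.

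The route in is ordinary. Entry needs a study-drug fill within 14 days of discharge from the PCI admission. A patient who fills ticagrelor on day 1 after discharge and clopidogrel on day 10 meets that requirement. Appendix A assumes that the drug filled is the drug begun in hospital, and for this patient that may well be false.

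Two things are at stake. People who change drug within days usually have a reason, so they are a selected group. Their first days of follow-up may also carry over the effect of the previous drug. If such changes went more often toward one study drug than the other, the hazard ratio would absorb the difference.

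**Working it through.** **Step 1. Trace the patient (ticagrelor day 1, clopidogrel day 10).**

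| Step | Looks at | Removes the patient? |
|---|---|---|
| Washout, 5.2 and 6.1 | prasugrel, clopidogrel | No |
| Prior-use steps, 5.3 | clopidogrel, prasugrel | No |
| More than one exposure category, 5.3 | the two study drugs | No |
| Exclusion 12 | thienopyridines, 5 days before admission | No: other drug class, and the window closes before discharge |
| Exclusion 13 | not implemented | No |

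**Step 2. Look for an unlisted step.** From the flowchart:
- Optum: 61,330 − (3,135 + 535 + 18 + 2 + 1,811 + 5,341 + 416 + 3,974 + 0 + 886 + 1 + 394 + 687 + 1,755 + 2,927) = 61,330 − 21,882 = 39,448.
- MarketScan: 91,281 − (3,653 + 958 + 20 + 0 + 2,457 + 7,235 + 265 + 3,739 + 0 + 2,039 + 1 + 654 + 235 + 2,041 + 1,981) = 91,281 − 25,278 = 66,003.

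Both final counts reproduce, so the printed steps account for every exclusion.

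**Step 3. What Table 1 may show.** Two rows are labelled as prasugrel use, one on the cohort entry date and one 180 to 1 day before.

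| Pooled | Clopidogrel arm | Prasugrel arm |
|---|---|---|
| Entry date, unmatched | 846 (1.0%) | 205 (0.9%) |
| 180 to 1 day before, unmatched | 840 (1.0%) | 225 (1.0%) |
| Entry date, matched | 194 (0.9%) | 204 (0.9%) |
| 180 to 1 day before, matched | 206 (0.9%) | 224 (1.0%) |

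These cannot be prasugrel. Use on the entry date should be close to 100% in the prasugrel arm, and earlier use should be close to zero after the flowchart removed 535 and 958 prior users. The pooled exposure column of the same table is headed with ticagrelor, so stale labels are plausible.

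If the rows are ticagrelor (assumption), prior use in the matched arms is 206/21,932 = 0.94% and 224/21,932 = 1.02%. The overlap between the two rows is not given. With no overlap, use on or before entry would be at most (206 + 194)/21,932 = 1.82% and (224 + 204)/21,932 = 1.95%.

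**Step 4. Illustrative effect on the hazard ratio.** Suppose prior users have twice the event rate of others (assumption). The rate ratio is then multiplied by (1 + p_prasugrel)/(1 + p_clopidogrel), where p is the share of prior users.
- Shares from step 3: 1.0102/1.0094 = 1.0008, about 0.1%.
- All prior users in one arm, 1% against 0: 1.01, that is 1%.

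**Step 5. Cost in power.** Power = Φ(|ln HR| × √(events/4) − 1.96), with HR 0.8 and the Section 10 event counts taken as given. The plan's figures reproduce. For example, pooled: 0.2231 × √(2,274.787/4) − 1.96 = 3.36, giving 0.9996. The losses below are assumed, at unchanged risk.

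| | Stated | 1% lost | 2.13% lost | 5% lost |
|---|---|---|---|---|
| Pooled | 0.9996 | 0.9996 | 0.9995 | 0.9994 |
| Optum | 0.885 | 0.882 | 0.878 | 0.868 |
| MarketScan | 0.984 | 0.984 | 0.983 | 0.980 |

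**The case against.** The best defence is that new use is defined relative to the two drugs compared, and that extending it to a third agent is a design preference. That is fair as far as it goes. But the plan itself made ticagrelor a censoring event, and it already removes prior users of the other study drug at a similar frequency: 535/58,195 = 0.9% in Optum and 958/87,628 = 1.1% in MarketScan. Consistency favours a baseline rule.

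A reader might infer four stronger things that the documents do not support.

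- *That the propensity score neither measures nor balances ticagrelor.* No row carries that label, but the two mislabelled rows may be exactly that. Section 9 puts the complete covariate list, apart from laboratory values, into the score.
- *That the Section 9 censoring figures show the scale.* The 596/21,932 = 2.72% and 339/21,932 = 1.55% are events after entry and include nursing home admission. They say nothing about use before entry.
- *That exclusion 12 is deficient.* It maps the trial's thienopyridine criterion, and ticagrelor is not a thienopyridine.
- *That refills by a patient already on ticagrelor escape censoring.* The wording refers to starting the drug, while the Section 9 table describes a switch. This is ambiguous, and no missed case is shown.

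It also stands that a pharmacy-claims washout cannot see ticagrelor given in hospital and changed before discharge.

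**Conclusion.** The gap is real. As written, the rules admit recent ticagrelor users as new initiators into a primary analysis that censors at ticagrelor. The documents show an open route, not a demonstrated bias, and they give no count of prior users.

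The effect is probably small. That judgement assumes the two mislabelled Table 1 rows are ticagrelor, in which case prior use is about 1% per arm and balanced after matching. Under a doubled event rate the hazard ratio would then move by about 0.1%. If the rows are something else, the frequency and balance of prior use are unknown.

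The inconsistency is firmest for the as-treated analysis. For the intention-to-treat analysis, Section 6.3.2 drops censoring for switching and discontinuation and does not say whether ticagrelor censoring stays.

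**What to change.** 1. Add to the washout in 5.2, 6.1 and the flowchart: no ticagrelor fill in the 180 days up to and including cohort entry. Report the number removed by arm and database.
2. Identify the drug in the two Table 1 rows and correct the labels.
3. Word the as-treated censoring event as any ticagrelor fill after entry.
4. Leave exclusion 12 as it is.

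The cost is one more exclusion on pharmacy claims already processed for censoring, followed by re-matching. If the mislabelled rows are ticagrelor, about 1% of patients would be lost, or just under 2% if no patient appears in both rows. Step 5 shows that this barely changes power. Ticagrelor given only in hospital would remain invisible and should be stated as a limitation.

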Marketscan: https://bwh-dope.aetion.com/projects/details/990/results/46158/result/0

Date conducted: December 15, 2019

In order to complete the initial power analysis, the dummy outcome of a 90-day gap in database enrollment will be used. This outcome is used to ensure that no information on the comparative risks of the outcomes of interest are available at this stage. Complete a 1:1 PS-matched comparative analysis using this outcome. PS should include only 3 covariates: age, sex, and combined comorbidity index. Power calculations are based on the formulas from Chow et al. (2008).

In order to complete the initial power analysis, the dummy outcome of a 90-day gap in database enrollment will be used. This outcome is used to ensure that no information on the comparative risks of the outcomes of interest are available at this stage.

Effectiveness research with Real World Data to support FDA's regulatory decision making: Protocol Template

Complete a 1:1 PS-matched comparative analysis using this outcome. PS should include only 3 covariates: age, sex, and combined comorbidity index. Power calculations are based on the formulas from Chow et al. (2008).

Reviewed by PI:	[name]	Date reviewed:	12/16/19
Reviewed by FDA:	[name]	Date reviewed:	1/2/20
Reasons for stopping			
analysis (if required):			

9. Balance Assessment after PS matching

Aetion report links (Prasugrel vs. clopidogrel):

Optum: https://bwh-dope.aetion.com/projects/details/989/results/46940/result/0
Marketscan: https://bwh-dope.aetion.com/projects/details/990/results/46941/result/0

Date conducted: 01/05/2020

After review of initial feasibility and power analyses, complete creation of the remaining covariates (see Table 1 below for list of covariates). Again, using the dummy outcome of a 90-day gap in database enrollment, complete a 1:1 PS-matched analysis. The PS should include the complete list of covariates (excluding laboratory values, which are missing in some patients).

• Provide plot of PS distributions stratified by treatment group.

Note- Please refer to Appendix B.

Report covariate balance after matching.

Note- For Table 1, please refer to Appendix B.

• Report reasons for censoring by treatment group.

  		
Overall	Referent	Exposure

Effectiveness research with Real World Data to support FDA's regulatory decision making

Dummy Outcome	0 (0.00%)	0 (0.00%)	0 (0.00%)
Death	123 (0.28%)	70 (0.32%)	53 (0.24%)

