4	Fibrin-specific fibrinolytic therapy less than 24 h before randomization	N/A	
5	Non-fibrin-specific fibrinolytic therapy less than 48 h before randomization	N/A	
6	Active internal bleeding or history of bleeding diathesis	Measured 180 days prior to drug initiation in any diagnosis position and inpetient or outputient setting For active internal bleading, refer to the sheet "Bleading"	Cunningham A, Stein CM, Chung CP, Daugherty JR, Smalley WE, Ray WA. An automated database case definition for serious bleeding related to oral anticoagulant use. Pharmacoepidemiol Drug Saf. 2011;20(6):560–566. doi:10.1002/pds.2109
7	Clinical findings, in the Judgment of the investigator, associated with an increased risk of bleeding	or Bleeding distribusis: ICD-9: 286.x Coagulation defects 287.x Purpura and other hemorrhagic conditions	Huybrechts KF, Gopalakrishnan C, Bartels DB, Zint K, Gurusamy VK, Landon J, et al. Safety and effectiveness of debigatran and other direct oral anticoagulants compared to warfarin in patients with atrial fibrillation. Clin Pharmacol Ther. 2019 Dec 23.
	Any of the following:		
	a) History of hemorrhagic stroke	Measured any time prior to index hospitalization in any diagnosis position, inpatient or outpatient setting Hemorrhagic stroke: ICD-9: 430.xx, 431.xx ICD-10: ICD.xx, IS1.xx,	2018;360:k119 http://dx.doi.org/10.1136/bmj.k119 Patorno, Elisabetta et al. "Empagliflozin and the Risk of Heart Failure Hospitalization In Routine Clinical Care: A First Analysis from the Empagliflozin Comparative Effectiveness and Safety (EMPRES) Study." Circulation. 2019 Apr 8. doi:
		Measured 180 days prior to drug initiation in any diagnosis position and inpatient or	10.1161/CIRCULATIONAHA.118.039177
8	b) Intracranial neoplasm, arteriovenous malformation, or aneurysm	outpatient setting Intracrantal reopiasm ICD-9: 191.x, 225.0, 225.2, 225.4 ICD-10: C71.x, D32.x, D33.x, AV matformation (of brain) ICD-9: 747.81 ICD-10: Q82.x Corobra Aneuryem ICD-9: 437.3 ICD-10: 167.1	
	c) Ischemic stroke within 3 months prior to screening	Measured 90 days prior to Index hospitalization in any position, inpatient setting, isohemic stroke:	Patorno, Elisabetta et al. "Cardiovascular outcomes associated with canagliflozin versus other non-giflozin antidiabetic drugs: population based cohort study," BMJ 2018;360:k19 http://dx.doi.org/10.1136/bmj.k119 Patorno, Elisabetta et al. "Empgliflozin and the Risk of Heart Failure Hospitalization

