Ischemic stroke (w and w/o mention of cerebral infarction); n (%)	2,399 (7.4%)	287 (4.2%)	0.14	2,470 (4.9%)	390 (2.6%)	0.12	4,869 (5.8%)	0,677 (3.1%)	0.13	
Hemorrhagic stroke; n (%)	1 (0.0%)	0 (0.0%)	#DIV/0!	1 (0.0%)	0 (0.0%)	#DIV/0!	2 (0.0%)	0 (0.0%)	#DIV/0!	
TIA; n (%)	480 (1.5%)	46 (0.7%)	0.08	523 (1.0%)	63 (0.4%)	0.07	1003 (1.2%)	109 (0.5%)	0.08	
Other cerebrovascular disease; n (%)	450 (1.4%)	43 (0.6%)	0.08	388 (0.8%)	46 (0.3%)	0.07	838 (1.0%)	89 (0.4%)	0.07	
Late effects of cerebrovascular disease; n (%)	396 (1.2%)	28 (0.4%)	0.09	291 (0.6%)	21 (0.1%)	0.08	687 (0.8%)	49 (0.2%)	0.09	
Cerebrovascular procedure; n (%)	16 (0.0%)	1 (0.0%)	#DIV/0!	34 (0.1%)	1 (0.0%)	0.04	50 (0.1%)	2 (0.0%)	0.04	
Heart failure (CHF); n (%)	6,838 (21.0%)	941 (13.7%)	0.19	7,137 (14.1%)	1,632 (10.7%)	0.10	13,975 (16.8%)	2,573 (11.7%)	0.15	
Peripheral Vascular Disease (PVD) or PVD Surgery ; n (%)	2,702 (8.3%)	361 (5.3%)	0.12	2,268 (4.5%)	413 (2.7%)	0.10	4,970 (6.0%)	0,774 (3.5%)	0.12	

Table 1: Prasugrel 10 mg vs Clopidogrel 75 mg

Atrial fibrillation; n (%)	4,283 (13.2%)	413 (6.0%)	0.25	4,104 (8.1%)	574 (3.8%)	0.18	8,387 (10.1%)	0,987 (4.5%)	0.22
Other cardiac dysrhythmia; n (%)	9,981 (30.7%)	1,632 (23.7%)	0.16	10,768 (21.2%)	2,653 (17.5%)	0.09	20,749 (24.9%)	4,285 (19.4%)	0.13
Cardiac conduction disorders; n (%)	4,606 (14.1%)	639 (9.3%)	0.15	4,344 (8.6%)	958 (6.3%)	0.09	8950 (10.7%)	1597 (7.2%)	0.12
Other CVD; n (%)	11,182 (34.3%)	1,890 (27.5%)	0.15	12,049 (23.7%)	3,160 (20.8%)	0.07	23,231 (27.9%)	5,050 (22.9%)	0.12
Diabetes-related complications									
Diabetic retinopathy; n (%)	742 (2.3%)	140 (2.0%)	0.02	641 (1.3%)	152 (1.0%)	0.03	1,383 (1.7%)	0,292 (1.3%)	0.03
Diabetes with other ophthalmic	61 (0.2%)	6 (0.1%)	0.03	426 (0.8%)	109 (0.7%)	0.01	0,487 (0.6%)	0,115 (0.5%)	0.01
manifestations; n (%)									
Retinal detachment, vitreous hemorrhage,	15 (0.0%)	1 (0.0%)	#DIV/0!	15 (0.0%)	4 (0.0%)	#DIV/0!	30 (0.0%)	5 (0.0%)	#DIV/0!
vitrectomy; n (%)									
Retinal laser coagulation therapy; n (%)	63 (0.2%)	11 (0.2%)	0.00	103 (0.2%)	28 (0.2%)	0.00	166 (0.2%)	39 (0.2%)	0.00
Occurrence of Diabetic Neuropathy; n (%)	2,028 (6.2%)	331 (4.8%)	0.06	1,485 (2.9%)	353 (2.3%)	0.04	3,513 (4.2%)	0,684 (3.1%)	0.06
Occurrence of diabetic nephropathy with ICD10 ; n (%)	1,915 (5.9%)	238 (3.5%)	0.11	994 (2.0%)	203 (1.3%)	0.05	2,909 (3.5%)	0,441 (2.0%)	0.09
Hypoglycemia; n (%)	396 (1.2%)	71 (1.0%)	0.02	608 (1.2%)	138 (0.9%)	0.03	1,004 (1.2%)	0,209 (0.9%)	0.03

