median [IQR]	0.00 [0.00, 0.00]	0.00 [0.00, 0.00]	0.00	0.00 [0.00, 1.00]	0.00 [0.00, 1.00]	0.00	0.00 (1.60)	0.00 (1.73)	0.00
Number of Ambulatory Blood pressure									
monitoring tests									
mean (sd)	0.00 (0.02)	0.00 (0.02)	0.00	0.00 (0.03)	0.00 (0.02)	0.00	0.00 (0.03)	0.00 (0.02)	0.00
median [IQR]	0.00 [0.00, 0.00]	0.00 [0.00, 0.00]	0.00	0.00 [0.00, 0.00]	0.00 [0.00, 0.00]	0.00	0.00 (0.03)	0.00 (0.02)	0.00
N of days on antihypertensive									
medications during baseline									
mean (sd)	67.42 (76.28)	67.51 (76.88)	0.00	62.89 (75.36)	62.70 (75.54)	0.00	64.30 (75.65)	64.20 (75.96)	0.00
median [IQR]	7.00 [1.00, 158.00]	7.00 [1.00, 161.00]	0.00	1.00 [1.00, 152.00]	2.00 [1.00, 153.00]	-0.01	2.87 (75.65)	3.56 (75.96)	-0.01
N of days in database anytime prior									
mean (sd)	1,616.01 (1,214.94)	1,629.92 (1,231.27)	-0.01	1,708.25 (1,223.37)	1,713.51 (1,215.39)	0.00	1679.50 (1220.75)	1687.46 (1220.36)	-0.01
median [IQR]	1,302.00 [622.00,	1,298.00 [631.00,	0.00	1,365.00 [681.00,	1,375.00 [702.00,	-0.01	1345.37 (1220.75)	1351.00 (1220.36)	0.00
	2,331.00]	2,369.00]		2,602.50]	2,609.00]				
Mean Copay for per prescription cost									
(charges in U.S. \$) (180-1 day prior)									
mean (sd)	24.78 (29.15)	25.15 (27.70)	-0.01	19.46 (24.18)	19.56 (23.85)	0.00	21.12 (25.83)	21.30 (25.11)	-0.01
median [IQR]	17.32 [6.94, 33.33]	17.92 [8.00, 33.33]	-0.02	13.33 [4.62, 26.99]	13.25 [5.00, 26.42]	0.00	14.57 (25.83)	14.71 (25.11)	-0.01
Missing; n (%)	1,195 (17.5%)	1,189 (17.4%)	0.00	2,793 (18.5%)	2,751 (18.2%)	0.01	3,988 (18.2%)	3940 (18.0%)	0.01
Colonos; n (%)	233 (3.4%)	218 (3.2%)	0.01	476 (3.2%)	473 (3.1%)	0.01	0,709 (3.2%)	691 (3.2%)	0.00
Fecal occult blood (FOB) test; n (%)	215 (3.1%)	216 (3.2%)	-0.01	432 (2.9%)	404 (2.7%)	0.01	0,647 (3.0%)	620 (2.8%)	0.01
Flu vaccine; n (%)	784 (11.5%)	787 (11.5%)	0.00	1,142 (7.6%)	1,140 (7.6%)	0.00	1,926 (8.8%)	1927 (8.8%)	0.00
Mammogram; n (%)	323 (4.7%)	309 (4.5%)	0.01	546 (3.6%)	540 (3.6%)	0.00	0,869 (4.0%)	849 (3.9%)	0.01
Pap smear; n (%)	141 (2.1%)	138 (2.0%)	0.01	362 (2.4%)	347 (2.3%)	0.01	0,503 (2.3%)	485 (2.2%)	0.01
Pneumonia vaccine; n (%)	716 (10.5%)	723 (10.6%)	0.00	678 (4.5%)	649 (4.3%)	0.01	1,394 (6.4%)	1372 (6.3%)	0.00
PSA test or Prostate exam for DRE; n (%)	1,042 (15.2%)	1,040 (15.2%)	0.00	2,105 (13.9%)	2,048 (13.6%)	0.01	3,147 (14.3%)	3088 (14.1%)	0.01
Bone mineral density; n (%)	107 (1.6%)	105 (1.5%)	0.01	119 (0.8%)	103 (0.7%)	0.01	0,226 (1.0%)	208 (0.9%)	0.01

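### The default 180-day covariate window contains the index PCI stay and leaves longer held history unused; prior revascularization is the clearest gap, and no longer look-back is planned even as a sensitivity analysis.

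*Combined protocol and SAP*

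**What the plan says.** Section 6.2 defines the Combined Comorbidity Index as "measured over the default baseline covariate assessment period, defined as 180 days prior to and including index date" and calls this the default. For the rest it says: "Remaining covariates are defined only after the study has passed the initial feasibility analysis and the initial power assessment and are listed in Table 1" in Appendix B. Section 9 adds: "The PS should include the complete list of covariates (excluding laboratory values, which are missing in some patients".

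Most Table 1 rows state no window. Those that do largely fit the default: CCI and HAS-BLED are labelled 180 days, visit rows split at 30 and 31–180 days, and laboratory rows without a window equal their 6-month rows (HbA1c 3,678 in both for unmatched Optum clopidogrel). There are exceptions. Frailty and hypertension use 365 days, and exclusion 8a in Appendix A (hemorrhagic stroke) is "Measured any time prior to index hospitalization in any diagnosis position, inpatient or outpatient setting".

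The index date is the study-drug fill within 14 days of discharge from the PCI stay (Section 5.3; Appendix A, key time points), so the 180 days include that stay. Table 1 also reports "N of days in database anytime prior". Section 13.2 plans one secondary analysis, PS trimming with decile adjustment, and no change of look-back.

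**The concern.** Two things follow from a short window that ends after the index admission.

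First, older disease counts only if it is coded again in the window. Before the index stay there were few occasions for that. In the matched pooled cohort, 2.1% (clopidogrel) vs 2.6% (prasugrel) had a hospitalization 31–180 days before index, 10.5% vs 10.1% a cardiologist visit, and 47.2% vs 47.5% an internal or family medicine visit.

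Second, the index procedure can swamp a history variable. *Previous cardiac procedure* is 98.5% in both matched arms, which is the index PCI and not history. The row labelled for the PS joins it to *History of CABG or PTCA* and so cannot separate patients with earlier revascularization from those without.

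Before matching, recorded vascular history is more common in clopidogrel users: any stroke 5.8% vs 3.1%, PVD 6.0% vs 3.5%, CKD 9.3% vs 4.8%. If unrecorded history followed that pattern, survived matching and raised MACE risk, the HR would lean towards prasugrel, which is the direction of the trial result being replicated (HR 0.81).

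A smaller point of the same kind: the stroke covariate is "Ischemic stroke (w and w/o mention of cerebral infarction); n" (%), so prior infarction is not balanced separately from occlusion without infarction.

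**Working it through.** **1. Unused history (Table 1, PS-matched).** Prior database time in days:

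| Arm | Lower quartile | Median | Lower quartile − 180 |
|---|---|---|---|
| Optum clopidogrel | 622 | 1,302 | 442 |
| Optum prasugrel | 631 | 1,298 | 451 |
| MarketScan clopidogrel | 681 | 1,365 | 501 |
| MarketScan prasugrel | 702 | 1,375 | 522 |

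The subtraction assumes that the count runs to the index date and so includes the 180 days. All four lower quartiles exceed 365, so a 365-day window would fall within prior database time for at least 75% of each arm. The row does not say that this time is continuous enrollment.

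**2. Recorded history after matching (pooled, 21,932 per arm).** SMD = (p0 − p1)/√{[p0(1−p0) + p1(1−p1)]/2}, clopidogrel minus prasugrel:

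| Row | Clopidogrel | Prasugrel | SMD |
|---|---|---|---|
| Any stroke | 667 (3.0%) | 677 (3.1%) | −0.003 |
| TIA | 117 (0.5%) | 109 (0.5%) | 0.005 |
| PVD | 746 (3.4%) | 772 (3.5%) | −0.006 |
| CKD | 1,033 (4.7%) | 1,057 (4.8%) | −0.005 |
| Old MI | 1,702 (7.8%) | 1,746 (8.0%) | −0.007 |

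These agree with Table 1 to its rounding. What is recorded is balanced.

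**3. Prior revascularization after matching.**
- Merged row labelled for the PS, pooled: 21,673 (98.8%) vs 21,661 (98.8%).
- *History of CABG or PTCA*, Optum: 1,761/6,835 (25.8%) vs 1,624/6,835 (23.8%), SMD 0.046 (Table 1: 0.05).
- MarketScan: 2,106 (13.9%) vs 1,980 (13.1%), Table 1: 0.02.
- Pooled: 3,867 (17.6%) vs 3,604 (16.4%), SMD 0.032 (Table 1: 0.03).

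**4. Precision.** Expected events by database (Section 10) are 801.47 + 1,361.45 = 2,162.92. SE(log HR) ≈ 2/√2,162.92 = 0.043. With the plan's own pooled count of 2,274.79 it is 0.042.

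**5. Illustrative size.** Bias factor = [1 + p0(r−1)]/[1 + p1(r−1)], where p0 and p1 are the prevalences of missed history in clopidogrel and prasugrel and r is its MACE ratio. None of these is in the documents.
- p0 = 3%, p1 = 2%, r = 1.5: 1.015/1.010 = 1.005. HR 0.81 reads 0.806; ln(1.005)/0.043 ≈ 0.1 SE.
- p0 = 5%, p1 = 2%, r = 2: 1.05/1.02 = 1.029. HR 0.81 reads 0.787; about 0.7 SE.
- Wider grid: p0 from 2% to 10%, p1/p0 of 0.53 (unmatched stroke ratio) or 0.80 (near the unmatched old-MI ratio), r = 1.5 or 2. HR 0.81 reads 0.808 to 0.775. The extreme corner (10%, 0.53, r = 2) has a factor of 0.957 on the HR, about one SE. The next largest is 0.978, about 0.5 SE.

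**6. The recorded revascularization imbalance, same formula.** Optum, r = 1.5 to 2: 1.1288/1.1188 = 1.009 to 1.2576/1.2376 = 1.016. The latter is 0.016/0.071 ≈ 0.2 of the Optum SE (2/√801.47 = 0.071).

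**The case against.** The strongest reply is that a fixed, uniform window is a defensible design and that the adjustment set is rich. Stroke, TIA, late effects of cerebrovascular disease, old MI, PVD and CKD are all listed, and Section 9 puts the complete list except laboratory values into the PS. The index stay is itself an occasion on which chronic conditions are coded. Matching on age, CCI, frailty and many drug classes would also carry along some unrecorded history. Pneumonia, expected to be null, gives a check on residual confounding. All of this stands.

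Three stronger readings are tempting and are not supported:

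- A reader might infer that every covariate uses only 180 days. Frailty and hypertension use 365 days. The stroke, MI and PVD rows state no window, so 180 days is inferred for them from the word default. The any-time rule for hemorrhagic stroke is an exclusion criterion and does not set a standard for covariates.
- A reader might infer that remote stroke, MI and vascular disease go unadjusted. Step 2 shows that the recorded forms balance. Only history with no claim in the window is at issue.
- A reader might infer a known bias towards prasugrel. The prevalence gaps cited for that are from before matching. The 5% vs 2% case supposes a ratio of 2.5 after matching, whereas recorded stroke plus TIA rows before matching give (5,873/83,351)/(786/22,059) = 1.98. With that ratio, p1 = 2% and r = 2, the factor is 1.019, about 0.4 SE.

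Look-back over all available time also has a real cost. Quartiles run from 622 to 2,331 days in matched Optum clopidogrel, so ascertainment would differ widely between patients. That tells against making it the sole primary definition, though not against a fixed longer window or a sensitivity analysis.

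The reply does not answer the revascularization point. A row at 98.8% in both arms cannot adjust for earlier CABG or PCI. Section 9 may mean that *History of CABG or PTCA* also enters separately, but the row labels suggest that the merged term replaces it, and the documents do not settle which.

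**Conclusion.** The plan holds more history than its default window uses, has no analysis to show whether that matters, and describes prior revascularization for the PS in a form that cannot discriminate. The first two rest on the 180-day default, the 622-day lower quartile and the single secondary analysis in Section 13.2. The third rests on the 98.8% row and on the remaining 25.8% vs 23.8% in Optum, which is a small standardized difference (0.05).

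The size and direction of any residual bias cannot be obtained from the documents. For one missed history at 3–5% vs 2% and r of 1.5–2.0 it is below one SE of the pooled log HR. It reaches about one SE only if 10% of clopidogrel patients have missed history, the full unmatched stroke ratio survives matching, and r is 2. This justifies a targeted repair and a sensitivity analysis. It does not show that the planned primary estimate is materially biased.

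**What to change.** Before outcomes are analysed (the Section 13 date is blank):

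1. Measure prior CABG/PCI strictly before the index admission and enter it in the PS as its own term, apart from the index procedure.
2. Split the ischemic stroke covariate into cerebral infarction and occlusion without infarction.
3. State the look-back for every Table 1 row.
4. Pre-specify a sensitivity analysis that measures chronic history (MI, stroke/TIA, PVD, heart failure, CKD, AF) over 365 days or all available time before the index admission. Keep days in database in the PS, rematch, and report balance and the HR beside the 180-day version.

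The cost is some reprogramming and one rematch; redefining covariates excludes no patients from the cohort. Under all-available look-back, ascertainment time varies between patients, but its mean is balanced between arms (1,679.50 vs 1,687.46 days, St. Diff. −0.01). A fixed 365-day window largely avoids that variation.
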